4. INTERIM ANALYSIS

Not applicable.

5. APPENDICES

5.1. Statistical methods details

5.1.1. General Linear Model

5.1.1.1. For continuous data

A model that will be used for this study is the General Linear Model studying treatment effect with baseline gender and country (as fixed effect) as covariates:

$$Y_{ijkt} = \gamma X_{ijkt} + a_i + b_j + d_k + \varepsilon_{ijkt}$$

Where:

- Y_{ijkt} is the response from the t^{th} patient, of gender k , in country j , that received treatment i .
- X_{ijkt} is the baseline value of the analysed variable for the t^{th} patient, of gender k , in country j , that received treatment i .
- γ denotes the common slope of the baseline covariate.
- a_i denotes the intercept of the i^{th} treatment.
- b_j denotes the fixed effect of country j .
- d_k denotes the fixed effect of the gender k .
- $\varepsilon_{ijkt} \sim \text{iid } N(0, \sigma_\varepsilon^2)$ denotes the experimental unit error associated with the t^{th} patient of gender k , in country j , that received treatment i .

The model can also be written in matrix notation as:

$$Y = X\beta + \varepsilon$$

Where:

- Y is the vector of observations.
- X is the design matrix of the fixed effects and baseline factors.
- β is the unknown vector of the fixed effects and baseline factors.
- ε is the unobserved vector of independent and identically distributed random errors, such as $\varepsilon \sim N(0, R)$ where $R = \sigma_\varepsilon^2 I_n$.

Estimate:

The estimate $\hat{\beta}$ of β is given by:

$$\hat{\beta} = (X'X)^{-1} X'Y$$

$$\text{with } \text{Var}(\hat{\beta}) = (X'R^{-1}X)^{-1} = \hat{C}$$

Confidence interval and p-value:

The Sum of Squares using a Least-Squares-means contrast is used for computing the Sum of Squares under $H_0: L\beta = 0$ (where $L\beta$ denotes a linear estimable combination of the fixed effects).

The 95% confidence interval of $\hat{\beta}$ is given by:

$$L\hat{\beta} \pm t_{\hat{\nu}, 0.975} \sqrt{L\hat{C}L'}$$

Where:

- $\hat{\nu}$ denotes the approximate degrees of freedom by Kenward Roger.
- $t_{\hat{\nu}, 0.975}$ is the 0.975th quantile of the t-distribution with $\hat{\nu}$ degrees of freedom.

The Least-Squares approach provides estimates of the linear parameters that are unbiased and have minimum variance among linear estimators.

The treatment effect is estimated by the difference of the Least-Squares-means of each studied treatment group.

Validation of hypothesis:

For the validation of the model used, the following points will be studied:

a) Normality and homoscedasticity of residuals

The assumptions of normality and homoscedasticity of residuals will be investigated on the chosen final model using some graphs and descriptive statistics.

b) Detection of outliers

The detection will be done using graphics.

5.1.1.2. Robust General Linear Model using rank-based analysis

The rank-based analysis is analogous to the least-squares analysis except that the Euclidean distance to minimize is replaced by a different measure of distance that is based on the dispersion function of Jaeckel (ref. Rfit: Rank-based Estimation for Linear Models):

$$\hat{\beta} = \text{Argmin} \|Y - X\beta\|_{\varphi}$$

With $\|\cdot\|_{\varphi}$ the following measure of distance, R being the rank and φ the Wilcoxon score function:

$$\|u\|_{\varphi} = \sum_{i=1}^n \varphi\left(\frac{R(u_i)}{n+1}\right) u_i$$

As such analysis cannot be implemented directly from SAS, the function *rfit* of the package Rfit of R will be used. Of note that only the phase 2 analysis set (see Section 5.1.2) will be performed in R.

5.1.2. Pattern imputation based

We will implement a hybrid approach using control-based pattern imputation and standard multiple imputation depending on the treatment group and the reasons of withdrawal.

Standard multiple imputation (Rubin, 1987) replaces each missing value with a set of plausible values that represent the uncertainty about the right value to impute. Each value is a Bayesian drawn from the conditional distribution of the missing observation given the observed data, made in such a way that the set of imputation properly represents the information about the missing value that is contained in the observed data for the chosen model.

The multiply imputed data sets are then analysed by using standard procedures for complete data and combining the results from these analyses, based on the change from baseline.

Multiple imputation inference involves 3 consecutive phases (phase 1: imputation step, phase 2: analysis step and phase 3: combination step).

1/ PHASE 1: Imputation step

To guarantee the reproduction of results, the seed will be fixed at 95008.

This part will be divided in 3 steps summarized hereafter:

| | Dataset | |
|----------------|--|---|
| Starting point | init (N incomplete rows) | Initial incomplete dataset |
| Step1: | DATA_BASIS (N*m incomplete rows) | Impute intermittent missing data (arbitrary) - MI approach based on MCMC method |
| Step2a: | | Impute data for all placebo patients and S95008 patients with a WD due to other reasons - classical MI imputation, with treatment, baseline, covariates, and time points of interest in the regression model |
| Step2b: | | Impute data for S95008 patients with a WD due to AE or lack of efficacy with a jump-to-reference approach, with baseline, covariates and time points of interest in the regression model. |
| Step 3: | DATA_COMPLETE (N*m complete rows) | Assemble back all data together |

Step 1:

First, data collected post treatment withdrawal (if any) should be considered as missing. All intermittent missing data (*i.e.* with an arbitrary missing pattern) of baseline and variable of interest at the planned visits will be first imputed using a MI approach based on MCMC method (with single chain) by treatment groups, in case the initial dataset has not a strict monotone missing pattern.

A dataset is said to have a monotone missing pattern if missing values always occur at the end of data records; if we note $Y_i = (Y_{i,0}, Y_{i,1}, \dots, Y_{i,t}, \dots, Y_{i,T})$ the measured variable at each time t from baseline ($t=0$) to the end of the study ($t=T$) for an individual i , the missing pattern is monotone if, for all individuals and all times, if $Y_{i,t}$ is missing, then $Y_{i,t+1}$ is also missing and if $Y_{i,t}$ is not missing, then $Y_{i,t-1}$ is not missing also.

A total of 100 imputed partially completed datasets will be generated.

In case of patients with no data available at baseline and at any post baseline visit, a regression method will be used on the 100 imputed partially completed datasets to perform the imputation at the baseline visit only, using in this order: baseline covariates (*e.g.* country, gender), treatment in the model.

This dataset will serve as a basis for Step 2a and Step 2b (*DATA_BASIS*).

For the following step, the entry dataset will be sorted by imputation, by treatment and by patient.

Step 2:

In this sequence, remaining missing data of *DATA_BASIS* will be imputed. The treatment group and the reason for study or drug premature withdrawals have to be considered as the imputation rules will be different. For this imputation step, countries with less than 10 patients will be gathered to avoid strata with no observed values.

a) For all placebo patients and patients in S95008 arm with study or drug premature withdrawals due to other reasons:

To impute those missing data, all data will be considered (regardless of the treatment and of the reason of withdrawal) in order to benefit of all data available at each visit. However, at the end, only data (imputed or initially complete) from all placebo patients and data from S95008 patients, completers or with initially missing data due to other reasons will be considered (the other being imputed with jump-to-placebo method, as explained in step 2b).

A regression method will be used to perform the imputation, using in this order: baseline, baseline covariates (e.g. country, gender), treatment and variable of interest at the planned visits in the model. Of note, for imputing data of visit *i*, data up to visit *i-1* are to be considered for the imputation, even if the data of visit *i-1* already results of an imputation (this is taken into account in PROC MI with the order of the variables put in the VAR statement). This is applicable for variable of interest at each planned post-baseline visits.

Of note, for subgroup analysis, the subgroup should not be added as a covariate in the regression model.

b) For patients with study or drug premature withdrawals due to lack of efficacy or AE in S95008 arm

To impute those missing data, an input dataset will be prepared with data from all placebo patients (completers or with missing values regardless of the reason), and from S95008 patients, with missing data due to AE/lack of efficacy.

The jump-to-placebo approach will be set up for these patients' imputations, by using the %mistep macro from James Roger (<https://www.lshtm.ac.uk/research/centres-projects-groups/missing-data#dia-missing-data> , zip file MISTEP20180327).

A sequence of %mistep will be run, considering as the first model (for the first post-baseline visit): baseline baseline covariates (e.g. country, gender), treatment*. The subsequent model (for the second post-baseline visit) will include, in addition to variables included in the first model, the residuals of this first model (put at the end of the statement). The other subsequent models will be implemented in the same way.

**at each visit the treatment variable is derived such as the missing value in the S95008 will be imputed using the placebo arm as reference.*

This macro will be used because no SAS procedure are currently available to perform the jump to reference approach.

Step 3:

Finally we can assemble back all subjects with complete data: all patients from Step2a and remaining S95008 patients from Step2b (*DATA_COMPLETE*).

In case of imputed data at W026 (respectively W012 depending on the analysis) are outside of the endpoint ranges, the imputed data will be replaced by the boundary that was overpassed.

| Endpoint | Min | Max |
|--|-----|------|
| CARS2 total score | 15 | 60 |
| SRS2 total score | 0 | 195 |
| CGI-I | 1 | 7 |
| VABS II Adaptative Behavior Composite standard score | 20 | 160 |
| VABS II Communication domain standard score | 20 | 160 |
| VABS II Daily Living Skills Domain standard score | 20 | 160 |
| VABS II Socialisation Domain standard score | 20 | 160 |
| PedsQL total score | 0 | 2300 |
| PedsQL Physical functioning score | 0 | 800 |
| PedsQL Emotional functioning score | 0 | 500 |
| PedsQL Social functioning score | 0 | 500 |
| PedsQL School functioning score | 0 | 500 |
| PedsQL Psychosocial Health Summary score | 0 | 1500 |
| WHOQOL-Bref Physical Domain Score | 0 | 100 |
| WHOQOL-Bref Psychological Domain Score | 0 | 100 |
| WHOQOL-Bref Social Relations Domain Score | 0 | 100 |
| WHOQOL-Bref Environment Domain Score | 0 | 100 |
| EQ-5D-3L index score | 0 | 1 |
| EQ-5D-3L VAS | 0 | 100 |

2/ PHASE 2: Analysis step

The planned model will be applied to each of the 100 imputed datasets obtained at the previous step (*DATA_COMPLETE*). For each imputed dataset i ($i=1,2,\dots,m$), the estimate of the difference between groups and the associated standard error will be stored.

Of note that for CGI-I analysis, before this analysis step, the imputed data will be rounded to the nearest unit. Moreover, this analysis step will be done on the change from baseline (whereas imputations were done on visit's value).

3/ PHASE 3: Combination step

Statistical inferences will be generated by combining results from the 100 analyses using Rubin's formulae. The multiple imputation estimator of the difference between Bumetanide and placebo is the average of the individual 100 estimators. The variance of the estimator is the combination of the between- and within-imputation variability (Carpenter and Kenward, 2007).

| | Mean | Variance |
|----------------|--------------------------|------------------------------|
| Estimate | $\text{Mean}(\hat{O}_i)$ | $\text{Variance}(\hat{O}_i)$ |
| Standard error | $\text{Mean}(\hat{U}_i)$ | $\text{Variance}(\hat{U}_i)$ |

Let \hat{O}_i and \hat{U}_i be the point and variance estimates from the i th imputed data set, $i=1,2,\dots,m$. Then the point estimates for O from multiple imputations is the average of the m complete-data estimates:

$$\hat{O} = \frac{1}{m} \sum_{i=1}^m \hat{O}_i$$

Let \hat{U} be the within-imputation variance, which is the average of the m complete-data estimates:

$$\hat{U} = \frac{1}{m} \sum_{i=1}^m \hat{U}_i$$

and B be the between-imputation variance:

$$B = \frac{1}{m-1} \sum_{i=1}^m (\hat{O}_i - \hat{O})^2$$

Then the variance estimate associated with \hat{O} is the total variance:

$$T = \hat{U} + \left(1 + \frac{1}{m}\right)B$$

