1.3. Determination of sample size

The sample size was estimated to meet the primary endpoint defined as the change in CARS2 from baseline to 6 months using a two-sided Student's test.

With a total of 170 patients, statistical significance should be established with a power of 90% and a type-one error of 0.05 for an effect size of 0.5 between groups.

Assuming around 15% prematurely withdrawal rate, the total number of patients to be included is 200.

Missing data will be imputed using a reference based multiple imputation with a jump-to-reference approach or a standard multiple imputation depending on the reasons of withdrawal. Simulations were carried out to evaluate the impact of this procedure on power under various scenarios. The results on 1000 simulations have shown that power does not drop under 80% in the worst-case scenario.

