3.4.2. Primary efficacy endpoint

3.4.2.1. Primary analysis

Definition:

The primary estimand is defined according to the primary objective of the trial, which is to evaluate treatment effect:

- Taking into account the unfavorable outcome when patients are unable to continue taking the study drug due to an adverse event or for lack of efficacy.
- Independently of treatment discontinuations for non-medical reasons because those patients would have theoretically continued to be treated as planned in clinical practice.

The attributes of the primary estimand will be defined as following:

- Population: children and adolescents aged from 2 to less than 7 years old with Autism Spectrum Disorder.
- Variable: change in CARS2 total score from baseline to W026.
- Summary measure: difference in means.
- Intercurrent events:
 - Treatment discontinuation due to lack of efficacy or AE (*hypothetical strategy*):
 - For S95008 arm, the quantification of the treatment effect cannot ignore the situation where a patient can no longer tolerate or benefits from the treatment, from whom a continuation of the treatment would not be conceivable. Bumetanide is a treatment with a rapid onset and short duration of action. So, the assumption that the treatment benefit in patients who discontinue the active arm disappears immediately upon discontinuation is clinically meaningful. CARS2 values after this intercurrent event will be considered as missing and imputed using a reference based multiple imputation (“jump-to-reference” approach).
 - For placebo arm, it will be considered as if patients were stayed under placebo, and CARS2 values after the intercurrent event will be considered as missing and imputed using a multiple imputation (MAR approach).
 - Treatment discontinuation for other reason (*hypothetical strategy*): a reasonable question is what difference is attributable to treatment if no such events occurred namely if patients were stayed under their randomised treatment. CARS2 values after the intercurrent events will be considered as missing and imputed in both arms using multiple imputations (MAR approach).

Primary endpoint: the primary efficacy endpoint is defined as the change from baseline to W026 of the CARS2 total score.

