Primary analysis: bumetanide will be compared to placebo on the primary efficacy endpoint in the RS, using a General Linear Model (see Appendix 5.1.1.1) including the fixed, categorical effect of treatment, gender and country as well as the continuous fixed covariate of baseline value.

GENERAL LINEAR MODEL (ANCOVA): change = baseline country gender treatment [1]

The assumptions underlying the model, as for instance, the normality and homoscedasticity of residuals and detection of outliers, will be checked.

Missing data handling:

- For all study premature withdrawals due to other reasons as well as for study premature withdrawals due to lack of efficacy or AE in placebo arm, missing data will be imputed in both arms using a multiple imputation based on similar patients in the same treatment arm (missing at random assumption).
- For study premature withdrawals due to lack of efficacy or AE in S95008 arm, missing data will be imputed using a reference based multiple imputation with a jump-to-reference approach (*missing not at random assumption*).
Missing data as well as data considered as missing for the primary analysis due to the strategy used to handle intercurrent event will be imputed in the same way.

Multiple imputation inference involves 3 consecutive phases.

1/ Imputation step:

A total of 100 imputed complete data sets will be generated.

The imputation step of missing data with a monotone pattern will be separated in several sequences:

- For all patients with study or drug premature withdrawals due to other reasons as well as for patients with study or drug premature withdrawals due to lack of efficacy or AE in placebo arm, the regression method (adjusted on the same covariates as the model [1] and considering all longitudinal data of planned visits) will be used to impute missing data (*i.e.* based on patient completers under corresponding treatment arm).
- For patients with study or drug premature withdrawals due to lack of efficacy or AE in S95008 arm, the imputation step will be done sequentially for each time point t separately (W4, W12 and W26) based on placebo patients with non missing data at the timepoint t . The regression method will be adjusted on the same covariates as model [1] except the treatment variable (which is a modified variable in order to consider the placebo data as reference for imputation) and considering all longitudinal data of planned visits up to timepoint t .

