3.4.2.3. Supplementary analyses

- Treatment policy estimand:

The primary analysis will be repeated for the primary endpoint using all CARS2 values reported regardless of occurrence of treatment discontinuation.

In case of CARS2 values are still missing, the same imputation process as in the primary analysis will be performed for these individuals.

- Hypothetical estimand based on Mixed-effects Model for Repeated Measures

A Mixed-effects Model for Repeated Measures (MMRM) (see Appendix 5.1.3) using the longitudinal data at each planned post-baseline visit of the double-blind period (W004, W012 and W026) will be performed as if patients had continued their randomised treatment. In this analysis, all data occurring after all intercurrent events will be considered as missing. The comparison associated with the analysis will be the contrasts between Bumetanide and placebo for the change from baseline to W026 of the CARS2 total score. The model will include the fixed, categorical effects of country, gender, treatment, visit, treatment by visit interaction, country by visit interaction and gender by visit interaction as well as the continuous, fixed covariates of baseline and visit-by-baseline interaction:

*MMRM: change at each visit = baseline country gender treatment visit treatment*visit baseline*visit country*visit gender*visit [4]*

Statistical elements: the following elements will be provided in a summary table:

- Estimate (standard error) of the difference between adjusted treatment arm means.
- Two-sided 95% CI of the estimate.

- W012 analysis:

The primary analysis will be repeated for the CARS2 total score expressed in term of change from baseline to W012.

- CARS2 responders analysis:

Definition:

CARS2 responders will be defined as patients having an improvement of at least 4.5 points in the CARS2 total raw score as compared to baseline (Jurek *et al.*, 2021).

Main Analysis:

CARS2 responders at W012 and at W026 will be analysed using a logistic regression model with the fixed categorical effect of treatment, country and gender.

Note: In case of a complete separation of data (zero cell count in a treatment group), only descriptive statistics will be provided. In case of quasi-completed separation of data, a logistic regression with penalized maximum likelihood will be used (see Appendix 5.1.4).

Missing data handling:

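### Step 2b of the primary imputation centres the bumetanide AE/lack-of-efficacy withdrawers' residuals on themselves, so a poor course before stopping is dropped for bumetanide but kept for placebo

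*SAP*

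**What the plan says.** SAP 5.1.2 splits the imputation by arm and by reason for withdrawal.

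- **Step 2a** covers all placebo patients, and bumetanide patients who withdrew for other reasons. In this step "all data will be considered (regardless of the treatment and of the reason of withdrawal) in order to benefit of all data available", and each visit is regressed on baseline, covariates, treatment and the child's own earlier scores. Only the relevant rows are kept afterwards.
- **Step 2b** covers bumetanide patients who withdrew for an adverse event or lack of efficacy. Its dataset is "all placebo patients (completers or with missing values regardless of the reason), and from S95008 patients, with missing data due to AE/lack of efficacy". The first visit model has baseline, covariates and treatment. The next one adds "the residuals of this first model (put at the end of the statement", and later ones follow suit. A footnote says that "the treatment variable is derived such as the missing value in the S95008 will be imputed using the placebo arm" as reference. It does not state the coding for bumetanide values observed before stopping.

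SAP 3.4.2.1 describes the same step as "based on placebo patients with non missing data at the timepoint", using longitudinal data up to that visit. It does not mention residuals. The estimand in that section is meant to count the unfavourable outcome of these patients, and it assumes that "the treatment benefit in patients who discontinue the active arm disappears immediately upon discontinuation is clinically meaningful".

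**The concern.** In jump-to-reference imputation, the mean moves to placebo once treatment stops, and the child's earlier deviation from his or her own arm is carried along through the residuals. Step 2b uses residuals, so it sets out to do this. But bumetanide completers and other-reason withdrawers are absent from its dataset. The only bumetanide rows at W004 and W012 belong to the withdrawers, so their residuals are deviations from each other and not from the arm.

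Placebo patients who stop for the same reasons are imputed from their actual earlier scores. If lack-of-efficacy stoppers were scoring badly before they stopped, that counts against placebo but not against bumetanide. The step feeds the primary estimate, its confidence interval and the only p-value that the SAP plans (3.4.1). The same datasets feed the CARS2 responder analysis, and the same approach serves SRS-2 and CGI-I.

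**Working it through.** **Scale.** SAP 1.3 gives effect size 0.5, 90% power, two-sided 0.05 and "Assuming around 15% prematurely withdrawal rate". These figures reproduce: 85 per arm gives 170 (power 0.903 by the normal approximation, 0.900 by the t test), and 170/0.85 = 200. The sample size is not in question; 0.5 SD is the yardstick.

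**Algebra.** Let the treatment indicator at a visit be 1 for observed bumetanide rows and 0 otherwise. The least-squares equation for its coefficient forces the residuals over the rows coded 1 to sum to zero. In the Step 2b dataset those rows are the withdrawers, so their mean residual is zero however badly they were doing. A lone observed withdrawer has a residual of exactly zero. Differences between withdrawers survive; the group's departure from its arm does not.

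**Size.** Relative to a fit with the whole bumetanide arm, the shift is about −p × b × D, where negative favours bumetanide and:
- p is the share of the bumetanide arm stopping for AE/lack of efficacy after a planned post-baseline CARS2;
- b is the regression of W026 on the last residual, about 0.65 here;
- D is the withdrawers' mean deviation from their arm, in SD of change, positive meaning worse.

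The documents give none of these, so all are assumed. The simulation used 100 per arm; CARS2 SD 5, 5.5, 6 and 6.5 at W000, W004, W012 and W026; correlations 0.5-0.75; SD of change 5.89; and 15% total withdrawal, with other-reason withdrawal unrelated to score. Analysis was by 100 imputations, ANCOVA on baseline and treatment (country and gender omitted) and Rubin's rules, with 8000 trials per no-effect scenario.

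| AE/LoE withdrawal | Before W004 | D | −p × b × D | Simulated shift (SD) | One-sided error as written |
|---|---|---|---|---|---|
| 5% | one third | 0.5 | −0.0333 × 0.65 × 0.5 = −0.011 | −0.011 | 2.2% |
| 5% | one third | 1.0 | −0.0333 × 0.65 × 1.0 = −0.022 | −0.023 | 3.1% |
| 10% | one third | 0.5 | −0.0667 × 0.65 × 0.5 = −0.022 | −0.023 | 2.2% |
| 10% | one third | 1.0 | −0.0667 × 0.65 × 1.0 = −0.043 | −0.044 | 3.3% |
| 10% | none | 0.95 | −0.100 × 0.65 × 0.95 = −0.062 | −0.062 | 5.1% |

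With the whole arm in the residual models, one-sided error was 1.3-1.9%. The simulation error near 2.5% is √(0.025 × 0.975/8000) = 0.17 percentage points. With D = 0 the shift is 0.000; with D = −0.5 and 10% withdrawn it is +0.023. As fractions of the planned effect, 0.011/0.5 = 2% and 0.062/0.5 = 12%.

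**Second simulation.** This used a common correlation of 0.6, 5-15% such withdrawals (half after W004, half after W012), and withdrawers about 0.7-1.6 SD worse than their arm, baseline-adjusted. With no true effect, the Step 2b rows gave −0.015 to −0.064 SD and whole-arm rows −0.003 to +0.004. The withdrawers' imputed W026 level relative to the placebo arm, baseline-adjusted, was:
- bumetanide, Step 2b rows: −0.02 to +0.02 SD;
- bumetanide, whole-arm rows: +0.24 to +0.61 SD;
- placebo, through Step 2a: +0.25 to +0.61 SD.

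**The other reading.** If the visit models are fitted on placebo only, as 3.4.2.1 can be read, residuals are deviations from the placebo mean. There is no shift when there is no true effect. But an earlier benefit is then part of the residual and is carried forward. At a true −0.50 SD this keeps about 0.01 SD (5% withdrawn) to 0.02-0.03 SD (10%) that jump-to-reference should remove, for example −0.47 against −0.45.

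**The case against.** **The defect depends on a coding that the SAP does not state.** The footnote covers only missing bumetanide values, and the behaviour of the macro lies outside the documents. That stands, but it does not rescue the plan. Coding every row as placebo removes the centring and then conflicts with the assumption that benefit vanishes on stopping. Each reading needs correcting.

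**The effect is small, and the larger figures need a large D.** At D = 0.5 the error is 2.2%, under 2.5%. D near 1.0 means withdrawers about 5.6-5.9 CARS2 points worse than their arm (0.95 or 1.0 × 5.89), more than the SAP's 4.5-point responder threshold. Many stopping criteria in Protocol 5.6.1 are laboratory, renal or ECG findings with no stated link to CARS2, so the pooled D may be modest. Part of the contrast in error rates is also conservatism of the whole-arm version. All of this stands and limits the weight of the point.

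**Supplementary analyses give a check.** Protocol 4.2.2 schedules a W026 CARS2 for most children who stop early, if background care is not importantly changed. The treatment-policy analysis uses those values, and the MMRM avoids Step 2b altogether. These checks are only partial. For values still missing under treatment policy, "the same imputation process as in the primary analysis will be performed for these individuals"; the MMRM answers a different question; neither carries a p-value.

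**The arms are meant to differ, and nothing requires residuals from the whole-arm mean.** The intended difference is in the mean after stopping. Nothing in the SAP explains why the deviation before stopping should be kept in one arm and dropped in the other.

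**Conclusion.** The concern holds. With observed visits coded as bumetanide, the Step 2b input rule removes the withdrawers' average departure from their arm, while Step 2a keeps it for placebo. This part follows from the text and from least squares.

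The size rests on assumed withdrawal rates, correlations and D. In the scenarios with worse-scoring withdrawers, the shift is 0.011-0.062 SD toward bumetanide, and one-sided error runs from 2.2% (no excess) to 5.1%. It applies only to withdrawers with a post-baseline CARS2, is nil at D = 0, and reverses when withdrawers were doing better. The placebo-only reading of 3.4.2.1 fails differently, by retaining up to about 0.03 SD of benefit at a true effect of 0.5 SD. The shift is modest, but it sits in the one confirmatory test and should be fixed before unblinding. Confidence is medium, because the coding and the withdrawal pattern are not in the documents.

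**What to change.** Before unblinding, amend SAP 5.1.2, Step 2b:

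1. Fit the visit models on the on-treatment CARS2 values of all randomised patients.
2. Code treatment visit by visit: bumetanide at visits observed before stopping, placebo from the first missing visit.
3. Keep only the imputed rows of the bumetanide AE/lack-of-efficacy patients, as Step 2a already does for its own subset.
4. Reword the second imputation bullet of SAP 3.4.2.1 to match, stating that earlier visits enter as residuals from each child's own arm.

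The cost is SAP wording and one dataset filter; no new data are needed. The estimate may become slightly less favourable. Simulated power at a true 0.5 SD (1500 trials per scenario) falls from about 93% to 90% with 10% such withdrawals and D = 0.5, and from about 93% to 91% with 5% and D = 0.5.
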